1.0 Background

By 2050, approximately 20% of the US population, or >80 million people, will be 65 y of age or older.¹ Unfortunately, aging is accompanied by a progressive reduction in the maximal strength, speed, and especially power of skeletal muscle. These age-related physiological changes often lead to functional limitations that are highly predictive of disability, institutionalization, and mortality in the elderly.^{2,3} Thus, any intervention that significantly enhances muscle contractile function could potentially improve the health, quality of life, and possibly even the longevity of older individuals.

Numerous factors undoubtedly account for the decline in muscle function described above, with age-related changes in the size, properties, and neural control of muscle likely all playing a role.⁴ Another important factor, however, may be a fall in NO bioavailability with aging. Although initially identified as a vasodilator, i.e., as “endothelium-derived relaxing factor”, NO is in fact a key cellular signaling molecule with pleiotropic effects in many tissues. These include skeletal muscle, wherein among other effects NO helps modulate contractile function.⁵⁻⁹ With aging, however, whole-body NO production decreases, as evidenced, e.g., by a progressive decline in the plasma concentrations of its downstream metabolites, NO_2^- and NO_3^- .^{10,11} In skeletal muscle itself, there is a dramatic decrease in interstitial NO_2^- and NO_3^- concentrations,¹² as well as a decline in the activity of the neuronal form of NO synthase (nNOS, or NOS1),^{13,14} the primary isoenzyme within muscle responsible for the synthesis of NO from L-arginine, O_2 , and NADPH. These changes are accompanied by an age-related reduction in flow-mediated vasodilation,¹⁵⁻¹⁸ perhaps the hallmark indicator of NO bioavailability. In turn, the latter (i.e., flow-mediated vasodilation) has been shown to correlate positively with muscular power and physical functioning in older men and women.¹⁹ Taken together, these data suggest that decreased NO production may contribute to the age-associated decline in muscle contractile properties and hence in functional capacity.

In this context, the physiological effects of dietary NO_3^- are of considerable interest. It is now recognized that, rather than being metabolically inert or, worse, a potential carcinogen, NO_3^- in the diet is a significant source of NO in the body²⁰⁻²⁴ (Fig. 1). In fact, this dietary pathway, which entails the reduction of NO_3^- to NO_2^- by facultative anaerobic bacteria in the mouth followed by further reduction of NO_2^- to NO by, e.g., deoxyhemoglobin, can account for as much as ~25% of basal whole-body NO production.^{25,26} This dietary pathway serves as an important “backup” system to the more well-known NOS pathway. This is likely to be especially true in skeletal muscle, since unlike the NOS pathway the dietary pathway operates well at low pO_2 and is stimulated rather than inhibited by low pH,²⁰⁻²⁴ conditions that regularly exist in muscle, both at rest and especially during contractile activity. Indeed, skeletal muscle has recently been shown to play a central role in whole-body $\text{NO}_3^-/\text{NO}_2^-/\text{NO}$ metabolism.^{27,28}

Figure 1. Enterosalivary pathway of NO production. From Ref. 22.

Based on the above, it is logical to hypothesize that increased dietary NO_3^- intake might enhance NO bioavailability in older men and women, leading to an improvement in

muscle function. Indeed, we have observed significant increases in muscle speed and power following dietary NO_3^- intake in healthy younger subjects,²⁹ athletes,³⁰ and especially middle-aged heart failure patients.³¹ (See Preliminary Data.) Along the same lines, Haider and Folland³² and Whitfield et al.³³ have reported that dietary NO_3^- intake enhances the rate of force development and peak force output of the quadriceps muscle of healthy young men during electrically-stimulated contractions. To date, however, no study has specifically examined the impact of dietary NO_3^- on muscle contractile function in older persons. Furthermore, it cannot be automatically assumed that dietary NO_3^- will be equally efficacious in older subjects. For example, in rodents the effects of dietary NO_3^- are more prominent in fast- vs. slow-twitch muscle,^{34,35} and some,³⁶⁻³⁹ but not all,⁴⁰⁻⁴² studies of humans have found that aging results in a reduction in the percentage of fast-twitch muscle fibers. Alternatively and/or in addition, more rapid destruction of NO due to increased production of reactive oxygen species by aging muscle⁴³ could limit the beneficial effects of dietary NO_3^- in older persons.

Even if the efficacy of a particular dose of NO_3^- could be established in older subjects, this would not necessarily mean that it is the optimal dose. There is limited data in the literature regarding the dose-response relationship for dietary NO_3^- for various outcomes, and only one study has examined the response to exercise over a wide range of doses.⁴⁴ These authors found that acute ingestion of either 8.4 or 16.8, but not 4.2, mmol of NO_3^- improved performance equally during high intensity *aerobic* exercise in healthy young men. However, it is not known whether a similar plateau exists with respect to improvements in muscle contractile function, nor is it known whether aging influences this relationship. Such information is obviously critical to any attempt to pursue funding for larger (e.g., multicenter) trials evaluating dietary NO_3^- as a potential treatment for reduced muscle function in older persons, especially since the incidence of negative side effects (e.g., GI distress) may increase at higher doses.

Our Preliminary Data (see below) suggest that older subjects may require a greater dose of NO_3^- than younger individuals to yield a significant improvement in muscle speed and/or power.

Preliminary data

Using methods essentially identical to those to be employed in the proposed experiments (see below), we previously demonstrated that acute dietary NO_3^- intake increased maximal knee extensor speed (Vmax) and power (Pmax) in 12 healthy, younger men and women by $11\pm 5\%$ ($P<0.05$) and $6\pm 3\%$ ($P<0.05$), respectively.²⁹ We observed similar dietary NO_3^- -induced improvements in muscle speed and power in 13 athletes performing multi-joint, multi-muscle, i.e., sprint cycling, exercise.³⁰ Lastly, we found even greater increases in Vmax and Pmax (of $12\pm 5\%$, $P=0.09$, and $13\pm 4\%$, $P<0.05$, y) in nine middle-aged patients with systolic heart failure (HF).³¹

[figure not shown]
Using the same methods, we have also recently determined the effects of dietary NO_3^- in six healthy men and women 64-79 y of age. As shown in Table 1, plasma NO_3^- and NO_2^- and breath NO increased ($P<0.05$) by $1309\pm 188\%$, $268\pm 91\%$, and $142\pm 19\%$, respectively, by 2 h after ingestion, and all three remained elevated for the remainder of the experiment. These findings are consistent with our previous research.²⁹⁻³¹ This increase in NO bioavailability resulted in a $9\pm 5\%$ increase in maximal muscle speed, i.e., Vmax (Fig. 2, *left panel*), with five out of the six subjects demonstrating an improvement. This increase, however, was not statistically significant (i.e., $P=0.13$), and maximal muscle power, i.e., Pmax, improved on average by only $2\pm 3\%$.

Table 1. Changes in plasma NO_3^- and NO_2^- and breath NO in response to dietary NO_3^- intake in older study participant.

	Trial	Pre	1 h	2 h	10 min post exercise
Plasma NO_3^- ($\mu\text{mol/L}$)	Placebo	26 \pm 4	24 \pm 3	24 \pm 3	22 \pm 4
	Nitrate	31 \pm 7	285 \pm 27*	295 \pm 27*	282 \pm 33*
Plasma NO_2^- ($\mu\text{mol/L}$)	Placebo	0.21 \pm 0.03	0.26 \pm 0.06	0.26 \pm 0.06	0.20 \pm 0.03
	Nitrate	0.27 \pm 0.04	0.43 \pm 0.13	0.49 \pm 0.06*	0.56 \pm 0.10*
Breath NO (ppb)	Placebo	23 \pm 5	26 \pm 4	27 \pm 4	23 \pm 5
	Nitrate	27 \pm 4	49 \pm 7*	38 \pm 4*	52 \pm 10*

Values are mean \pm S.E. for n=7. *Nitrate trial significantly higher than Placebo trial at same time point (P<0.05).

(P=0.47) (Fig. 2, *center panel*). This is only 1/3rd as much as we previously found in younger Figure 2. Responses of Vmax (left panel) and Pmax (center and right panels) to dietary NO_3^- in older subjects.

men and women.^{29,30} Closer examination of the data suggested that this diminished effect was due to an inadequate dose of NO_3^- , as there was a significant positive relationship between NO_3^- intake relative to body mass and the relative improvement in Pmax (Fig. 2, *right panel*). These preliminary results therefore suggest that older individuals remain responsive to NO_3^- , but that a higher dose may be required to elicit improvements in muscle contractile function.

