2.0 Rationale and Specific Aims

In light of the above, we will use a double-blind, placebo-controlled, crossover design to address the following Specific Aim:

Specific Aim #1: To determine the dose-response relationship between acute dietary NO_3^- supplementation and muscle contractile function in healthy, older (i.e., 65-79 y old) men and women.

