On Study Day 2, participants will undergo phlebotomy for plasma NO_3^- and NO_2^- measurement, and have their breath NO level determined. (Breath NO will be measured as a biomarker of increases in whole-body NO production in response to dietary NO_3^- intake.^{52,53}) The subject will then ingest 3.3 mL/kg of a commercial concentrated beetroot juice (BRJ) supplement (Beet It Sport®, James White Drinks, Ipswich, UK) either: 1) essentially devoid of NO_3^- (placebo); 2) containing (as determined by previous direct measurement) 91 $\mu\text{mol}/\text{mL}$ NO_3^- (thus total dose = 300 $\mu\text{mol}/\text{kg}$, or 21 mmol in a 70 kg subject); or 3) an equal mixture of the placebo and NO_3^- -containing BRJ products. The placebo, which is prepared by the company by extracting NO_3^- from BRJ using an ion exchange resin, is indistinguishable in packaging, color, taste, texture, and smell from the standard product, and does not alter plasma $\text{NO}_3^-/\text{NO}_2^-$ or breath NO concentrations or the physiological responses to exercise.²⁹⁻³¹ Additional blood and breath samples will be obtained 1 and 2 h later, as well as blood pressure and heart rate, after which time the subject will have the Vmax and Pmax of the knee extensor muscles of their dominant leg determined via isokinetic dynamometry (see below). The timing of all measurements has been chosen to correspond to peak plasma $\text{NO}_3^-/\text{NO}_2^-$ concentrations and breath NO levels, which reach a maximum 2-3 h after ingestion.²⁹⁻³¹

On Study Days 3 and 4, participants will be asked to return to undergo the same studies as described above for Study Day 2.

Study Methods

Measurement of NO₃⁻ in each batch of BRJ w/ or w/o NO₃⁻: The NO₃⁻ content of each batch of BRJ w/ or w/o NO₃⁻ will be determined using high performance liquid chromatography (HPLC) (ENO-30, Eicom USA, San Diego, CA).

Measurement of plasma NO₃⁻, NO₂⁻, and breath NO: Venous blood samples will be obtained prior to consumption of BRJ w/ or w/o NO₃⁻ and every hour thereafter for 3 hours, plasma rapidly separated by centrifugation, and frozen at -80° C until subsequently analyzed for NO₃⁻ and NO₂⁻ concentration using HPLC as described above. Breath NO levels will be measured at the same time points using a portable electrochemical analyzer (NIOX VERO, Circassia Pharmaceuticals, Chicago, IL).

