Measurement of skeletal muscle contractile function: A Biodex 4 system will be used to measure each subject's muscle contractile properties as previously described.²⁹⁻³¹ Briefly, subjects will perform maximal knee extensions with their dominant leg at angular velocities of 0, 1.57, 3.14, 4.71, and 6.28 rad/s. (Not all older individuals may be able to achieve the highest velocity – if not, the highest measured angular velocity and associated torque will be used in all subsequent calculations.) The subject will perform 3-4 knee extensions at each velocity, with 2 min of rest allowed between each set of contractions. To eliminate artifacts, data will be “windowed” to isolate the isokinetic phase and smoothed using a 9 point weighted moving average filter. The highest torque generated at each velocity will be used to calculate peak power at that velocity, after which the resulting power-velocity curve will be fit to a polynomial function to determine the subject's maximal knee extensor velocity (Vmax) and corresponding power (Pmax). Subsequently, the subject will perform an “all out” 50 contraction fatigue test (at 3.14 rad/s) to determine whether dietary NO₃⁻ influences fatigue resistance (i.e., increases average power) during repetitive, maximal activation. Finally, recovery of muscle function will be quantified by measuring restoration of torque during knee extensions performed periodically over the next 10 min.

Risks

Likely: The insertion of an intravenous tube for blood drawing is associated with a small amount of discomfort. The subjects are likely to notice reddish urine or stools after drinking beetroot juice or control. This is normal and not harmful.

Less Likely: The insertion of an intravenous tube for blood drawing is associated with a small risk of bleeding or infection. After the EKG, some people may experience a skin rash but this usually goes away without treatment.

Rare: The risk of arrhythmia and heart attack are rare and the risk of death during exercise testing is extremely rare. The risk of heart attack is <0.1% in all patients undergoing exercise testing (and should be lower in these subjects since they have no coronary artery disease). The risk of death is reported as less than 2/10,000 tests or <0.02%.

Mitigation of Risks

Blood draw: Only trained staff will place IVs and collect blood samples

EKG: trained nurses will prepare the skin for the EKG and place the electrodes.

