Although the proposed study will provide important new information regarding the effect of NO_3^- dose on muscle contractile function in older individuals, it will not address the mechanism(s) responsible for any improvements that may be observed. While clearly relevant, answering such questions are beyond the scope of the present investigation.

Finally, we note that historically there have been concerns that increased NO_3^- intake may lead to formation of carcinogenic nitrosamines.⁶⁹ However, the Joint FAO/WHO Expert Committee on Food Additives has concluded that "Overall, the epidemiological studies showed no consistently

increased risk for cancer with increasing consumption of NO_3^- .⁶³ Furthermore, diets high in vegetables, such as the DASH diet widely recommended to hypertensive patients, routinely exceed the WHO acceptable daily intake of NO_3^- by >5-fold. In contrast, the amount of dietary NO_3^- shown to improve exercise tolerance in previous studies is only slightly above the WHO limit.⁷⁰ Nonetheless, the safety and efficacy of increased dietary NO_3^- would need to be established in follow-up large-scale, longer-term studies before BRJ or other NO_3^- -rich foods or could be widely recommended to older individuals.

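### GI distress is named as possibly dose-related, but the Risks list omits it, no dosing-day procedure asks about symptoms, and no tolerability summary by dose is planned

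*Combined protocol and SAP*

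**What the plan says.** Section 1.0 explains why dose matters. The main reason is efficacy: "it is not known whether a similar plateau exists with respect to improvements in muscle contractile function", and the effect of aging on that relationship is also unknown. Side effects come in as a further reason: "especially since the incidence of negative side effects (e.g., GI distress) may increase at higher doses". The single aim in section 2.0 concerns efficacy: "To determine the dose-response relationship between acute dietary NO_3^- supplementation and muscle contractile function in healthy, older" men and women.

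Section 5.0 sets three drinks of equal volume per kg: placebo, a full-strength product ("thus total dose = 300 $\mu\text{mol}/\text{kg}$, or 21 mmol in a 70 kg subject"), and "an equal mixture of the placebo and NO_3^- -containing BRJ products". After ingestion on Day 2 the schedule reads "Additional blood and breath samples will be obtained 1 and 2 h later, as well as blood pressure and heart rate", followed by dynamometry; Days 3 and 4 repeat this. No symptom question appears. Under Risks, the only effect listed for the drink is discoloration: "The subjects are likely to notice reddish urine or stools after drinking beetroot juice or control". The other entries concern blood drawing, the EKG and exercise testing.

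Section 6.0 defines an adverse event broadly enough to include any symptom, related or not, and provides for grading and attribution. Section 7.0 describes a mixed-model ANOVA of individual endpoints and contains no adverse-event or tolerability summary.

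**The concern.** The protocol raises a dose-related side effect as part of its case for studying dose, then makes no arrangement to observe it. Two things are at stake.

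First, the trial is meant to prepare for larger studies. Choosing a dose for those is easier if benefit and acute tolerability are described at the same levels in the same people. Mild, passing nausea or cramping is the kind of symptom that unprompted reporting may miss.

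Second, Vmax, Pmax and the 50-contraction fatigue test depend on voluntary effort, and section 7.0 explains that voluntary exercise was preferred to electrical stimulation. Testing starts about 2 h after the drink, in fasted participants. If GI discomfort reduced effort at the full dose, the response could look flatter than it is, resembling the plateau that section 1.0 wants to identify. No planned record would show whether symptoms were present. This mechanism is plausible but not demonstrated: the documents give no GI event rate and no evidence of an effect on effort.

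**Working it through.** **1. The sections side by side**

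| Topic | Where | What is there |
|---|---|---|
| GI distress may rise with dose | 1.0 Background | Stated, as an added reason for dose information |
| Risks of the drink | 5.0 Risks | Discoloration only |
| Dosing-day assessments | 5.0 Study Procedures | Blood, breath NO, blood pressure, heart rate, dynamometry |
| How adverse events are elicited | 6.0 | Not stated |
| Adverse events linked to study day or dose | 6.0 | Not stated |
| Summary by dose | 7.0 | None |

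**2. Dose levels that a table would use.** The stated dose reproduces: 3.3 mL/kg × 91 µmol/mL = 300.3 µmol/kg, and 300.3 × 70 / 1000 = 21.0 mmol at 70 kg. The equal mixture gives half: 150 µmol/kg, or 10.5 mmol at 70 kg. Each participant is scheduled for all three drinks, so every comparison is within-subject and the placebo separates nitrate from juice.

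**3. What solicited data could show.** The plan gives no tolerability figure to reproduce. Inputs are n = 20 (enrolled, section 3.0) and n = 15 (the number section 7.0 calls sufficient, with 20 allowing for drop-out). All event rates below are assumptions, because the documents state none.

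- *Upper bound after zero events*, one-sided 95%: 1 − 0.05^(1/n). For n = 20 this is 13.9%; for n = 15 it is 18.1%. The upper limit of a two-sided 95% exact interval, 1 − 0.025^(1/n), is 16.8% and 21.8%.
- *Chance of at least one event* at an assumed true rate of 10%: 1 − 0.9^n = 88% for n = 20 and 79% for n = 15.
- *Formal paired test, full dose against placebo* (exact McNemar, two-sided 0.05). If all discordant pairs favor one side, five give p = 2 × 0.5^5 = 0.0625 and six give p = 2 × 0.5^6 = 0.031, so at least six are needed. With discordance in one direction only, power is P(Binomial(n, p) ≥ 6). The last row allows discordance both ways.

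| Assumed discordance (symptom on full dose only vs placebo only) | n = 20 | n = 15 |
|---|---|---|
| 20% vs 0% | 0.20 | 0.06 |
| 30% vs 0% | 0.58 | 0.28 |
| 40% vs 0% | 0.87 | 0.60 |
| 30% vs 5% | 0.32 | 0.17 |

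A test would detect only very large differences. The useful output is counts by dose with exact intervals.

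**The case against.** The strongest reply is that the plan never undertakes to measure tolerability. The critical information in section 1.0 is whether the muscle benefit plateaus; GI distress is a subordinate reason, worded as a possibility. If half the dose works as well, an efficacy result alone makes the higher dose unnecessary. Section 7.0 calls the study a pilot and defers safety and efficacy to larger, longer-term studies. Section 6.0 already counts any symptom as an adverse event, and since each participant takes all three drinks on separate days, events that came to notice could be listed by dose afterwards.

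Most of this stands. It rules out treating tolerability as a missing endpoint, and it means the added data would be descriptive. It does not answer the narrower point: section 6.0 leaves elicitation and the link to dose unspecified, and the Risks list does not match the Background.

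A reader might also take the remark in section 7.0 that the nitrate amount "shown to improve exercise tolerance in previous studies is only slightly above the WHO limit" as reassurance about the drink that this trial's full dose undercuts. The text does not support that use. The paragraph addresses carcinogenic nitrosamines, not GI effects. Comparing 21 mmol with the earlier doses cited in section 1.0 (21/8.4 = 2.5; 21/16.8 = 1.25) says nothing about how often GI symptoms occur.

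**Conclusion.** The point holds as a modest gap that is cheap to close. The protocol names a possibly dose-related side effect, omits it from Risks, and has no planned, systematic way to describe it by dose or alongside the effort-dependent tests. The efficacy analysis is not invalidated.

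Two stronger conclusions that a reader might draw are not supported:

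- *That the trial cannot inform the balance of benefit and tolerability.* Spontaneously reported symptoms fall under section 6.0 and could be tabulated by dose, though mild ones may be missed.
- *That participants are not told of GI distress.* The consent form was not available for review, so disclosure cannot be assessed; only the protocol's own Risks list can.

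The size of the gain is limited. With every participant asked, zero events at a dose would bound the rate at about 14% (n = 20) or 18% (n = 15), one-sided 95%. These bounds assume complete follow-up at the stated n. The power figures rest on assumed discordance rates.

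**What to change.** 1. Reconcile Risks in section 5.0 with section 1.0: list GI distress, or say why it is left out. Check that the consent form agrees.
2. On Days 2 to 4, ask one fixed GI symptom and severity question, with participant and staff still blinded, at time points already in the schedule: before the drink, at 1 h, at 2 h just before dynamometry, and at the end of the visit.
3. State in section 6.0 that adverse events are asked about at each visit and recorded by study day, so they can be matched to dose after unblinding.
4. Add to section 7.0 one table of symptom counts and severity for placebo, half and full dose, with exact (Clopper-Pearson) intervals, shown beside Vmax and Pmax and labeled descriptive, with no hypothesis test.

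The cost is one case-report-form item, one table and a few lines of amended text, with no added visits or samples. The drawback is that prompting will produce more mild reports; the placebo day gives the background against which to read them.

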2.0 Rationale and Specific Aims

In light of the above, we will use a double-blind, placebo-controlled, crossover design to address the following Specific Aim:

Specific Aim #1: To determine the dose-response relationship between acute dietary NO_3^- supplementation and muscle contractile function in healthy, older (i.e., 65-79 y old) men and women.

